# A 4 Data protection

The ICF will incorporate wording that complies with relevant data protection and privacy legislation. In some cases, such wording will be in a separate accompanying document. AstraZeneca will not provide individual genotype results to patients, their family members, their general physician, any insurance company, any employer, or any other third party, unless required to do so by law.

Precautions are taken to preserve confidentiality and prevent genetic data from being linked to the identity of the patient. In exceptional circumstances, however, certain individuals might see both the genetic data and the personal identifiers of a patient. For example, in the case of a medical emergency, an AstraZeneca Physician or an Investigator might know a patient's identity and might also have access to his or her genetic data. Also, regulatory authorities may require access to the relevant files. Even so, the patient's medical information and the genetic files would remain physically separate.

Each patient will be assigned a unique identifier by the Sponsor. Any patient records or data sets transferred to the Sponsor will contain only the identifier; patient names or any information which would make the patient identifiable will not be transferred.

The patient must be informed that his/her personal study-related data will be used by the Sponsor in accordance with local data protection law. The level of disclosure must also be explained to the patient.

The patient must be informed that his/her medical records may be examined by Clinical Quality Assurance auditors or other authorized personnel appointed by the Sponsor, by appropriate IRB/IEC members, and by inspectors from regulatory authorities.

# A 5 Committees structure

The safety of all AstraZeneca clinical studies is closely monitored on an on-going basis by AstraZeneca representatives in consultation with Patient Safety. Issues identified will be addressed; for instance this could involve amendments to the Clinical Study Protocol and letters to Investigators.

# A 6 Dissemination of clinical study data

Any results both technical and lay summaries for this trial, will be submitted to EU CTIS within a year from global End of Trial Date in all participating countries, due to scientific reasons, as otherwise statistical analysis is not relevant.

A description of this clinical study will be available on

http://astrazenecagrouptrials.pharmacm.com and http://www.clinicaltrials.gov as will the summary of the main study results when they are available. The clinical study and/or summary of main study results may also be available on other websites according to the regulations of the countries in which the main study is conducted.

# A 7 Data quality assurance

All patient data relating to the study will be recorded on printed or electronic CRF unless transmitted to the Sponsor or designee electronically (eg, laboratory data). The Investigator is responsible for verifying that data entries are accurate and correct by physically or electronically signing the CRF.

The Investigator must maintain accurate documentation (source data) that supports the information entered in the CRF.

The Investigator must permit study-related monitoring, audits, IRB/IEC review, and regulatory agency inspections and provide direct access to source data documents.

The Sponsor or designee is responsible for the data management of this study including quality checking of the data.

Study monitors will perform ongoing source data verification to confirm that data entered into the CRF by authorized site personnel are accurate, complete, and verifiable from source documents; that the safety and rights of patients are being protected; and that the study is being conducted in accordance with the currently approved protocol and any other study agreements, ICH GCP, and all applicable regulatory requirements.

AstraZeneca or designee is responsible for medical oversight throughout the conduct of the study which includes clinical reviews of study data in accordance with the currently approved protocol. Monitoring details describing clinical reviews of study data from a medical perspective are included in more detail in the Medical Oversite Plan.

Records and documents, including signed ICFs, pertaining to the conduct of this study must be retained by the Investigator for 25 years after study completion unless local regulations or institutional policies require a longer retention period. No records may be destroyed during the retention period without the written approval of the Sponsor. No records may be transferred to another location or party without written notification to the Sponsor.

# A 8 Source documents

Source documents provide evidence for the existence of the patient and substantiate the integrity of the data collected. Source documents are filed at the Investigator's site.

Data reported on the CRF that are transcribed from source documents must be consistent with the source documents or the discrepancies must be explained. The Investigator may need to request previous medical records or transfer records, depending on the study. Also, current medical records must be available.

All information in original records and certified copies of original records of clinical findings, observations, or other activities in a clinical study necessary for the reconstruction and evaluation of the study, including interactive voice response system printouts, are defined as source documents. Source data are contained in source documents (original records or certified copies).

# A 9 Publication policy

The results of this study may be published or presented at scientific meetings. If this is foreseen, the Investigator agrees to submit all manuscripts or abstracts to the Sponsor before submission. This allows the Sponsor to protect proprietary information and to provide comments.

The Sponsor will comply with the requirements for publication of study results. In accordance with standard editorial and ethical practice, the Sponsor will generally support publication of multicenter studies only in their entirety and not as individual site data. In this case, a coordinating Investigator will be designated by mutual agreement.

# **B 2** Definitions of serious adverse event

A serious adverse event is an AE occurring during any study phase (ie, run-in, treatment, washout, follow-up), that fulfils one or more of the following criteria:

- Results in death
- Is immediately life-threatening
- Requires in-patient hospitalization or prolongation of existing hospitalization
- Results in persistent or significant disability or incapacity.
- Is a congenital anomaly or birth defect
- Is an important medical event that may jeopardize the patient or may require medical treatment to prevent one of the outcomes listed above.

Adverse Events (AEs) for malignant tumours reported during a study should generally be assessed as Serious AEs. If no other seriousness criteria apply, the 'Important Medical Event' criterion should be used. In certain situations, however, medical judgement on an individual event basis should be applied to clarify that the malignant tumour event should be assessed and reported as a Non-Serious AE. For example, if the tumour is included as medical history and progression occurs during the study, but the progression does not change treatment and/or prognosis of the malignant tumour, the AE may not fulfill the attributes for being assessed as serious, although reporting of the progression of the malignant tumor as an AE is valid and should occur. Also, some types of malignant tumours, which do not spread remotely after a routine treatment that does not require hospitalization, may be assessed as Non-Serious;

examples include Stage 1 basal cell carcinoma and Stage 1A1 cervical cancer removed via cone biopsy.

Malignant tumours that – as part of normal, if rare, progression – undergo transformation (e.g., Richter's transformation of B cell chronic lymphocytic leukemia into diffuse large B cell lymphoma) should not be considered a new malignant tumour.

# **B 3** Life threatening

'Life-threatening' means that the patient was at immediate risk of death from the AE as it occurred or it is suspected that use or continued use of the product would result in the patient's death. 'Life-threatening' does not mean that had an AE occurred in a more severe form it might have caused death (eg, hepatitis that resolved without hepatic failure).

# **B 4** Hospitalization

Outpatient treatment in an emergency room is not in itself a serious AE, although the reasons for it may be (eg, bronchospasm, laryngeal edema). Hospital admissions and/or surgical operations planned before or during a study are not considered AEs if the illness or disease existed before the patient was enrolled in the study, provided that it did not deteriorate in an unexpected way during the study.

# B 5 Important medical event or medical treatment

Medical and scientific judgement should be exercised in deciding whether a case is serious in situations where important medical events may not be immediately life threatening or result in death, hospitalization, disability or incapacity but may jeopardize the patient or may require medical treatment to prevent one or more outcomes listed in the definition of serious. These should usually be considered as serious.

Simply stopping the suspect drug does not mean that it is an important medical event; medical judgement must be used.

- Angioedema not severe enough to require intubation but requiring iv hydrocortisone treatment
- Hepatotoxicity caused by paracetamol (acetaminophen) overdose requiring treatment with N-acetylcysteine
- Intensive treatment in an emergency room or at home for allergic bronchospasm
- Blood dyscrasias (eg, neutropenia or anemia requiring blood transfusion, etc.) or convulsions that do not result in hospitalization
- Development of drug dependency or drug abuse

# **B 6 CTCAE** grade

The grading scales found in the revised NCI CTCAE version 4.03 will be utilized for all events with an assigned CTCAE grading. For those events without assigned CTCAE grades, the criteria recommended in the CTCAE manual that converts severity levels into CTCAE grades should be used. A copy of the CTCAE can be downloaded from the Cancer Therapy Evaluation Program website (http://ctep.cancer.gov). The applicable version of CTCAE should be described clearly.

It is important to distinguish between serious and severe AEs. Severity is a measure of intensity whereas seriousness is defined by the criteria in Appendix B 2. An AE of severe intensity need not necessarily be considered serious. For example, nausea that persists for several hours may be considered severe nausea, but not a SAE unless it meets the criteria shown in Appendix B 2. On the other hand, a stroke that results in only a limited degree of disability may be considered a mild stroke but would be a SAE when it satisfies the criteria shown in Appendix B 2.

# B 7 A guide to interpreting the causality question

When making an assessment of causality consider the following factors when deciding if there is a 'reasonable possibility' that an AE may have been caused by the drug.

- Time Course. Exposure to suspect drug. Has the patient actually received the suspect drug? Did the AE occur in a reasonable temporal relationship to the administration of the suspect drug?
- Consistency with known drug profile. Was the AE consistent with the previous knowledge of the suspect drug (pharmacology and toxicology) or drugs of the same pharmacological class? Or could the AE be anticipated from its pharmacological properties?
- De-challenge experience. Did the AE resolve or improve on stopping or reducing the dose of the suspect drug?
- No alternative cause. The AE cannot be reasonably explained by another etiology such as the underlying disease, other drugs, other host or environmental factors.
- Re-challenge experience. Did the AE reoccur if the suspected drug was reintroduced after having been stopped? AstraZeneca would not normally recommend or support a re-challenge.
- Laboratory tests. A specific laboratory investigation (if performed) has confirmed the relationship.

In difficult cases, other factors could be considered such as:

- Is this a recognized feature of overdose of the drug?
- Is there a known mechanism?

Causality of 'related' is made if following a review of the relevant data, there is evidence for a 'reasonable possibility' of a causal relationship for the individual case. The expression 'reasonable possibility' of a causal relationship is meant to convey, in general, that there are facts (evidence) or arguments to suggest a causal relationship.

The causality assessment is performed based on the available data including enough information to make an informed judgment. With limited or insufficient information in the case, it is likely that the event(s) will be assessed as 'not related'.

Causal relationship in cases where the disease under study has deteriorated due to lack of effect should be classified as no reasonable possibility.

# **B 8** Medication error, Drug abuse, Drug misuse

#### **Medication error**

For the purposes of this clinical study a medication error is an unintended failure or mistake in the treatment process for an IMP or AstraZeneca NIMP that either causes harm to the participant or has the potential to cause harm to the participant.

A medication error is not lack of efficacy of the drug, but rather a human or process related failure while the drug is in control of the study site staff or participant.

Medication error includes situations where an error.

- occurred
- was identified and intercepted before the participant received the drug
- did not occur, but circumstances were recognize that could have led to an error

Examples of events to be reported in clinical studies as medication errors:

- Drug name confusion
- Dispensing error (eg, medication prepared incorrectly, even if it was not actually given to the participant)
- Drug not administered as indicated, for example, wrong route, dose (error greater than +/- 10%), or wrong site of administration
- Drug not taken as indicated (eg, tablet dissolved in water when it should be taken as a solid tablet)
- Drug not stored as instructed (eg, kept in the fridge when it should be at room temperature)
- Wrong participant received the medication (excluding IVRS/IWRS errors)

• Wrong drug administered to participant (excluding IVRS/IWRS errors)

Examples of events that **do not** require reporting as medication errors in clinical studies:

- Errors related to or resulting from IVRS/IWRS including those which lead to one of the above listed events that would otherwise have been a medication error
- Participant accidentally missed drug dose(s) (eg, forgot to take medication)
- Accidental overdose (will be captured as an overdose)
- Participant failed to return unused medication or empty packaging
- Errors related to background and rescue medication, or standard of care medication in open label studies, even if an AZ product

Medication errors are not regarded as AEs but AEs may occur as a consequence of the medication error.

## Drug abuse

For the purpose of this study, drug abuse is defined as the persistent or sporadic intentional, non-therapeutic excessive use of IMP/study intervention or AstraZeneca NIMP for a perceived reward or desired non-therapeutic effect.

Any events of drug abuse, with or without associated AEs, are to be captured and forwarded to the DES using the Drug Abuse Report Form. This form should be used both if the drug abuse happened in a study participant or if the drug abuse regards a person not enrolled in the study (such as a relative of the study participant).

Examples of drug abuse include but are not limited to:

- The drug is used with the intent of getting a perceived reward (by the study participant or a person not enrolled in the study)
- The drug in the form of a tablet is crushed and injected or snorted with the intent of getting high.

## **Drug misuse**

Drug misuse is the intentional and inappropriate use (by a study participant) of IMP/study intervention or AstraZeneca NIMP for medicinal purposes outside of the authorised product information, or for unauthorised IMPs/study interventions or AstraZeneca NIMPs, outside the

intended use as specified in the protocol, and includes deliberate administration of the product by the wrong route.

Events of drug misuse, with or without associated AEs, are to be captured and forwarded to the DES using the Drug Misuse Report Form. This form should be used both if the drug misuse happened in a study participant or if the drug misuse regards a person not enrolled in the study (such as a relative of the study participant).

Examples of drug misuse include but are not limited to:

- The drug is used with the intention to cause an effect in another person
- The drug is sold to other people for recreational purposes
- The drug is used to facilitate assault in another person
- The drug is deliberately administered by the wrong route
- The drug is split in half because it is easier to swallow, when it is stated in the protocol that it must be swallowed whole
- Only half the dose is taken because the study participant feels that they were feeling better when not taking the whole dose
- Someone who is not enrolled in the study intentionally takes the drug.

# **Appendix C** Handling of human biological samples

# C 1 Chain of custody of biological samples

A full chain of custody is maintained for all samples throughout their lifecycle.

The Investigator at each center keeps full traceability of collected biological samples from the patients while in storage at the center until shipment or disposal (where appropriate).

The sample receiver keeps full traceability of the samples while in storage and during use until used or disposed of or until further shipment and keeps documentation of receipt of sample shipment.

AstraZeneca will keep oversight of the entire life cycle through internal procedures, monitoring of study sites, auditing or process checks, and contractual requirements of external laboratory providers

Samples retained for further use will be stored in the AZ-assigned biobanks and will be registered by the AstraZeneca Biobank Team during the entire life cycle.

If required, AstraZeneca will ensure that remaining biological samples are returned to the site according to local regulations or at the end of the retention period, whichever is the sooner.

# C 2 Withdrawal of Informed Consent for donated biological samples

AstraZeneca ensures that biological samples are returned to the source or destroyed at the end of a specified period as described in the informed consent.

If a patient withdraws consent to the use of donated biological samples, the samples will be disposed of/destroyed, and the action documented. If samples are already analyzed, AstraZeneca is not obliged to destroy the results of this research.

As collection of the biological sample(s) is an integral part of the study, then the patient is withdrawn from further study participation.

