# 7. DISCONTINUATION OF TREATMENT AND SUBJECT WITHDRAWAL

# 7.1 Discontinuation of study treatment

An individual patient will not receive any further IP (durvalumab, tremelimumab, or placebo) if any of the following occur in the patient in question:

• Withdrawal of consent from further treatment with IP. The patient is, at any time, free to discontinue treatment, without prejudice to further treatment. A patient who discontinues treatment is normally expected to continue to participate in the study

(eg, for safety and survival follow up) unless they specifically withdraw their consent to all further participation in any study procedures and assessments (see Section 7.3).

- An AE that, in the opinion of the Investigator or AstraZeneca, contraindicates further dosing
- Any AE that meets criteria for discontinuation as defined in the Dosing Modification and Toxicity Management Guidelines (see Section 8.4.5)
- Pregnancy or intent to become pregnant
- Non-compliance with the study protocol that, in the opinion of the Investigator or AstraZeneca, warrants withdrawal from treatment with IP (eg, refusal to adhere to scheduled visits)
- Initiation of alternative anticancer therapy including another investigational agent
- Clinical progression or RECIST 1.1-defined radiological progression (refer to Appendix F)

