# 7.3 Withdrawal from the study

Patients are free to withdraw from the study at any time (IP and assessments) without prejudice to further treatment.

Patients who withdraw consent for further participation in the study will not receive any further IP or further study observation, with the exception of follow-up for survival, which will continue until the end of the study unless the patient has expressly withdrawn their consent to survival follow-up. Note that the patient may be offered additional tests or tapering of treatment to withdraw safely.

A patient who withdraws consent will always be asked about the reason(s) for withdrawal and the presence of any AE. The Investigator will follow up AEs outside of the clinical study.

If a patient withdraws consent, they will be specifically asked if they are withdrawing consent to:

- All further participation in the study including any further follow up (eg, survival contact telephone calls)
- Withdrawal to the use of any samples (see Appendix C)

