## Withdrawal of consent for genetic research:

Patients may withdraw from this genetic research at any time, independent of any decision concerning participation in other aspects of the main study. Voluntary withdrawal will not prejudice further treatment. Procedures for withdrawal are outlined Appendix C 2.

Not applicable for China.

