#### **Informed consent**

The genetic component of this study is optional and the patient may participate in other components of the main study without participating in the genetic component. To participate in the genetic component of the study the patient must sign and date both the consent form for the main study and the genetic component of the study. Copies of both signed and dated consent forms must be given to the patient and the original filed at the study center. The Principal Investigator(s) is responsible for ensuring that consent is given freely and that the patient understands that they may freely withdrawal from the genetic aspect of the study at any time.

Not applicable for China.

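### Appendix C 2 removes a patient from the study for withdrawing sample consent and does not exempt optional samples, yet Appendix D 2 makes C 2 the procedure for leaving the optional genetic research

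*Protocol*

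**What the plan says.** **Protocol Appendix C 2** (withdrawal of consent for donated samples) has one trigger: the patient withdraws consent to the use of donated biological samples. The samples are then destroyed and this is documented. The section goes on: "As collection of the biological sample(s) is an integral part of the study, then the patient is withdrawn from further study participation". A list of investigator steps follows, covering notification, identification and destruction of the samples. Neither the sentence nor the list separates mandatory from optional samples.

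**Protocol Appendix D 2** (withdrawal of consent for genetic research) says: "Patients may withdraw from this genetic research at any time, independent of any decision concerning participation in other aspects of the main study". It adds: "Voluntary withdrawal will not prejudice further treatment". The next sentence is: "Procedures for withdrawal are outlined Appendix C 2". Under its informed consent heading, D 2 makes the Principal Investigator responsible for the patient's understanding that "they may freely withdrawal from the genetic aspect of the study at any time".

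**Protocol Section 8.7.1** makes the genetic sample optional and lets patients who refuse it stay in the study.

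**Protocol Section 7.3** has sites ask a withdrawing patient about two items. One is all further participation. The other is "Withdrawal to the use of any samples (see Appendix C".

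**The concern.** A patient who leaves only the optional genetic research is told by D 2 that main-study participation is a separate matter. The site is then sent to C 2, which says the patient leaves the study. The procedure named for a separable withdrawal therefore contains an instruction that makes it inseparable.

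Two things are at stake. The first is the integrity of a voluntary consent: the terms on which the patient agreed to give the genetic sample would not be honoured. The second is data. A patient wrongly taken out of the study could lose later RECIST scans and patient-reported outcomes, together with any study treatment still to come.

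The sponsor's rule for mandatory samples is not challenged.

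**Working it through.** No formula applies and the plan gives no figure to reproduce. The check is to follow one case through the current protocol text: a patient still in follow-up, with no progression, withdraws consent to the optional genetic sample and nothing else.

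1. **Starting point, Appendix D 2.** The withdrawal is allowed at any time and is independent of the main study. The weight falls on this independence sentence. The no-prejudice sentence is weaker evidence, because Sections 7.1 and 7.3 use similar wording for patients who stop study drug or leave the study, where it can only mean later care. D 2 then refers to C 2 as a whole.

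2. **Appendix C 2.** A genetic blood sample is a donated biological sample, so the trigger is met. The removal sentence follows. Its reason, that collection is integral, is stated as a fact about the samples. It is not framed as a condition, such as applying only where collection is mandatory. Read literally, the patient leaves the study.

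3. **Comparison with the rest of the protocol.**
   - Section 8.7.1 and Appendix D 2 call the genetic component optional. A reason that depends on collection being integral does not fit it.
   - Appendix A 3, on optional exploratory use of leftover samples, repeats the destruction step almost as in C 2 and stops there, with no removal.
   - Appendix A 3 and the study selection paragraph of D 2 say that refusing the genetic research carries no penalty and no exclusion from the main study. They concern refusing, not withdrawing later, but they show that the component is meant to be separable.
   - Section 7.3 lists sample use apart from full withdrawal, which also points to separability. However, it covers any samples and refers to Appendix C, so it leads to the same removal sentence.

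4. **What removal would mean in practice.** This is inferred, because C 2 does not say. Section 7.3 provides: "Patients who withdraw consent for further participation in the study will not receive any further IP or further study observation". That is written for patients who withdraw consent to further participation, which this patient has not done. Section 7.1 opens its list of reasons to stop study drug with: "An individual patient will not receive any further IP (durvalumab, tremelimumab, or placebo) if any of the following occur in the patient in question". That list does not include withdrawal of sample consent. If a site nonetheless handled the case under 7.3, scans and patient-reported outcomes would stop, as would any remaining treatment. Survival follow-up would continue unless the patient expressly refused it.

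Steps 1 and 2 give opposite answers on study participation for the same patient. Step 3 shows that D 2 is the answer the rest of the protocol supports.

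**The case against.** The strongest reply is that the documents already resolve the point. The removal sentence gives its own reason, and that reason is false for an optional sample. D 2 is the specific provision and states the outcome just before it refers to C 2. What it borrows is procedures, and the procedures in C 2 are notification and destruction; loss of study status is a consequence that D 2 has already ruled out. Section 7.3 keeps the two decisions apart. The consent form, which is not among the documents reviewed, may also state the rule.

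Most of this stands as evidence of intent: removal was probably meant for mandatory samples only. It does not cure the text. The limit has to be inferred, and the instruction in question ends a patient's participation. A clear consent form would reduce the risk, but the protocol would still say two things.

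A reader might also infer that each such patient costs one of the 370 PFS events, and hence some power. The documents do not support that:

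- Appendix D 2 says uptake of the genetic research is unknown, and no withdrawal rate is given anywhere.
- Under the first trigger in Section 9.2 the primary PFS analysis waits for about 370 events, so a lost event would normally be replaced by another patient's. The count could fall short only if one of the other two triggers came first.
- Patients in the combination arm do not count toward the 370, and the genetic research does not apply in China.

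Nor do the documents support reading C 2 as a stated ground for stopping study drug or as a loss of survival data, for the reasons in step 4 of the working.

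**Conclusion.** Wrong as written: an internal contradiction in current version 5.0 text, of low severity. Confidence is high for the wording. The practical consequence is inferred: it needs a site to apply C 2 literally against D 2 and then to treat the case as a Section 7.3 withdrawal.

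The number of patients affected cannot be estimated from the documents and is probably very small. No effect on power, type I error or the 370-event target is claimed. For an affected patient the likely loss is later scans and patient-reported outcomes. The case for correcting the text rests mainly on honouring a voluntary consent and giving sites one clear rule.

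**What to change.** In Appendix C 2, limit the removal sentence to mandatory samples and add, for example: *Withdrawal from the optional genetic research (Appendix D), or from any other optional sample or optional use of samples, leads only to destruction of those samples. Study treatment, RECIST scans, PRO, safety and survival follow-up continue unless the patient separately withdraws under Section 7.3.*

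In Appendix D 2, point the cross-reference only to the notification and destruction steps of C 2.

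The broader wording on optional samples is deliberate. Section 7.3 sends withdrawal for any sample to Appendix C, so the optional stool samples and optional biopsies in Section 8.8 meet the same sentence.

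The cost is a short addition to C 2 and one changed sentence in D 2 at the next amendment. No data collection, procedure or analysis changes, and the rule for mandatory samples stays as it is.
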